9.4.7 Biological Assessment of Child Immune Function

To supplement the information obtained on serious infections and hospitalizations and vaccination experience over the 5-year follow-up period for all live born children in the study, a biological sample sub-study will be offered to **subjects** in all 3 cohorts, to be overseen by a co-investigator. Eligible infants will be **at least 6 months of age, and preferably by 12 months of age** and will have had up to 3 diphtheria, tetanus, and pertussis scheduled immunizations. A small blood sample via heel stick **or venipuncture** will be collected in enrolled infants and sent to a single laboratory for analysis of IgG-tetanus antibody. Results of the test will be measured both continuously as well as classified as negative, indeterminate, or positive.

OTIS will communicate the result to the mother, and in those situations where the result is negative or indeterminate, the mother will be advised to share this result with her pediatrician, and OTIS will recommend repeating the test in approximately 1 year. The expectation is that near 100% of children in all 3 groups will test positive for immunity.

As this sample collection is most efficiently accomplished at the **contracted laboratory, the study will work with subjects to identify a local laboratory location for sample collection. If the subject is unable or unwilling to have the sample taken at the contracted laboratory, the sample may be taken at the** time of the dysmorphology examination. The study physicians will be tasked with collecting samples from infants whose mothers have consented. The dysmorphology exam for this study will be scheduled preferentially at or after 6 months of age and should coincide with the adequacy of immune response assessment. In the case where the dysmorphology exam is scheduled prior to 6 months, an additional appointment **may** be scheduled in order to collect samples for the adequacy of immune response assessment 6 to 12 months after delivery. **If it is not possible for the subject to have the sample taken by the contracted laboratory or the study dysmorphologist, the study will work with the subject to coordinate with the child's pediatrician or the laboratory associated with the pediatrician's office to collect the sample.**

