While it is anticipated that not all mothers will agree to this sub-study, a sample size of 60 in each group will be targeted, with preference given to recruiting exposed pregnancies that represent the distribution of length of exposure.

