9.5 Study Size

An enrollment total of 75 in the exposed group and 150 in each of the 2 comparison groups after 10 years is anticipated. Given that these numbers assume the prevalence of exposure is sufficient to support recruitment of these numbers, the feasibility of achievement will be re-evaluated at each annual interim review of the data.

Based on previous experience with MotherToBaby/OTIS Pregnancy Studies, we estimate that subjects will be an average of 7-10 weeks post-LMP at the time of enrollment. Given this mean gestational timing at enrollment, the anticipated spontaneous abortion/stillbirth rate is 10%, the estimated elective abortion rate is 5%, and the estimated lost to follow-up rate is 5%. This results in an estimated 71 observable pregnancies of which 60 are estimated to result in live births in cohort 1 (exposed group), and an estimated 142 observable pregnancies of which 120 are estimated to result in live births in cohorts 2 and 3 (control groups).

Baseline rates of major structural **birth** defects, spontaneous abortion, premature delivery, and small for gestational age, as well as the standard deviation for mean birth weight of full-term infants were based on previous MotherToBaby/OTIS studies and on general population data (Table 3). With the sample size estimated above, at $\geq 80\%$ power, alpha of 0.05, two-tailed tests of significance (except as noted below for pattern of minor structural **birth** defects), and each comparison group independently compared to the exposed group, the minimum effect sizes detailed in Table 3 will be detectable.

With respect to the evaluation of minor malformations, the strength of this study design is in the ability to examine the data for a pattern of minor and/or major structural **birth** defects, given that the known human teratogens are typically associated with a pattern as opposed to isolated major **structural** birth defects. A baseline prevalence estimate of 1% has been used for a specific pattern of minor **structural birth** defects. The RR detectable with this sample size is 10.0. This represents a 10% birth prevalence of a specific pattern (ie, approximately 6 children in the exposed sample), which is comparable to the birth prevalence of a specific pattern in other known human teratogens of moderate risk such as the anticonvulsant medications.

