For the primary outcome, the study is powered to detect that the Evolocumab-Exposed group has a 3.8-fold (or greater) risk of all major **structural** birth defects combined relative to the risk in the primary comparison group. This level of risk for teratogenicity is below that observed for other, but not all, agents deemed teratogenic. Importantly, known human teratogens tend to be associated with increased risks for specific patterns of birth defects and are not associated with increased risks for any and all major **structural birth** defects. For this reason, the analysis of the primary outcome, combined with evidence of a cluster or pattern of defects, provides the best ability for evaluation of teratogenic risk.

Table 3. Sample Size and Power for a Specified Effect Size Based on Minimal Sample Size^a

Outcome	N in Cohort 1	N in Cohort 2 or 3	Baseline Rate	RR	Power ^b
Major structural birth defects ^c	71	142	4% ^d	3.8	84%
Specific pattern of 3 or more minor structural birth defects	60	120	1% ^e	10.0	71% ^f
Spontaneous abortion/stillbirth	71	142	10% ^g	2.5	88%
Preterm delivery	60	120	9% ^h	2.8	85%
SGA	60	120	10% ⁱ	2.6	80%
Small for age (postnatal growth deficiency)	46	108	10%	2.8	82%
Neurodevelopmental outcomes (Phase II)	40	40	--	0.5 SD ^j	80%
Inadequate immune response (via IgG tetanus antibody status)	60	120 ^k	20% ^l	2	82%

Definitions: Ig = immunoglobulin; RR = relative risk; SGA = small for gestational age.

^a Software used to calculate power and effect size: OpenEpi v3 (Dean et al, 2015).

^b Based on Fisher's Exact Test or chi-square, two-tailed, alpha 0.05, except for specific pattern of 3 or more minor anomalies as noted below.

^c Primary endpoint.

^d Baseline rate in comparison group based on 4.1% in statin exposed (Winterfeld et al, 2013).

^e Baseline rate in comparison group expected to be 0-1% based on no evidence of a pattern.

^f Based on one-tailed Fisher's Exact Test, alpha 0.05.

^g Baseline rate based on 13.6% in statin exposed (Winterfeld et al, 2013) and 4.4% (Chambers et al, 2013) (rate influenced by gestational time of enrollment).

^h Baseline rate based on 16.1% (Winterfeld et al, 2013) and 6.2% (Toleikyte et al, 2011).

ⁱ Baseline rate based on 5.0% for low birth weight defined as < 5th centile which translates to 10% for SGA defined as < 10th centile (Toleikyte et al, 2011).

^j Minimum detectable difference calculated for neurodevelopmental outcomes as a continuous variable (instead of RR for categorical variables).

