^k Estimating 60 infants per cohort.

^l Baseline rate based on Marshall et al (2010).

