9.7.2.5.2 Secondary Analysis

The following will comprise the secondary analyses:

1. Comparison of all secondary outcomes between the Specific Evolocumab-Exposed cohort and Comparison Group I
2. Comparison of the primary and all secondary outcomes between the Specific Evolocumab-Exposed cohort and Comparison Group II

The comparison of the prevalence of the total proportion of major structural **birth** defects between the Specific Evolocumab-Exposed cohort and Comparison Group II will be among all live births and, separately, among all pregnancies excluding those lost to follow-up. The comparison of the prevalence of ≥ 3 minor malformations between the Specific Evolocumab-Exposed cohort and each of the 2 comparison groups will be among children who receive the dysmorphological examination. The comparison of IgG-tetanus antibody status (test negative or indeterminate vs test positive) by group (Exposed, Comparison Group I, Comparison Group II) among those in the biological sample sub-study.

In each cohort we will separately calculate the proportion of all pregnancies ending in live birth, spontaneous abortion, stillbirth, elective termination, and lost to follow-up; crude comparisons will be made between cohorts.

The evaluation for a pattern of minor structural **birth** defects will be conducted using the following steps:

1. A comparison among groups of the proportion of infants with any 3 or more minor structural **birth** defects will be made without regard to pattern
2. Among infants with 3 or more minor **structural birth** defects, the Evolocumab-Exposed group will be examined for evidence of a specific pattern of 3 or more defects in any 2 or more children. If such a pattern is identified, Comparison Groups I and II will be evaluated for any evidence of the same pattern.

In each cohort among all live born infants we will separately calculate the proportion of premature delivery, small for gestational age on weight, length or head circumference, and rates of serious infections, hospitalizations, adverse vaccine reactions, and adverse neurodevelopmental outcomes; crude comparisons will be made between cohorts.

Mean birth weight, length and head circumference for full-term live born infants will be compared between cohorts. Postnatal growth parameters will be compared using the proportion of infants ≤ 10 th centile for sex and age with respect to weight, height, or head circumference.

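### Table 3's 82% power for inadequate immune response pools the two comparison groups and assumes a 20% failure rate, and the protocol's own text contradicts both inputs

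*Protocol*

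**What the plan says.** The immune-response row of Table 3 in Protocol section 9.5 reads, in column order (outcome, exposed N, comparator N, baseline rate, relative risk, power in percent): "Inadequate immune response (via IgG tetanus antibody status) 60 120 ^k 20% ^l 2 82". The comparator column is headed for cohort 2 or cohort 3, that is, one comparison group at a time. Footnote k qualifies the 120: "Estimating 60 infants per cohort". The text introducing the table promises at least 80% power, two-tailed at 0.05, with "each comparison group independently compared to the exposed group". Footnote b names Fisher's exact test or chi-square.

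Section 9.4.7 describes the sub-study. Its sample size statement is: "While it is anticipated that not all mothers will agree to this sub-study, a sample size of 60 in each group will be targeted". Its expected result is: "The expectation is that near 100% of children in all 3 groups will test positive for immunity".

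Section 9.7.2.5.2 defines the analysis as "The comparison of IgG-tetanus antibody status (test negative or indeterminate vs test positive) by group", and lists the exposed group and Comparison Groups I and II separately. An indeterminate result therefore counts as inadequate, together with a negative one.

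**The concern.** Three inputs to the row disagree with the text around it.

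- **Comparator number.** Other rows of Table 3 also show 120, but there it is the expected live births in one comparison cohort. In this row footnote k makes it 60 + 60. No pooled comparison is planned in sections 9.5 or 9.7.2.5.2.
- **Baseline rate.** If nearly all children in every group test positive, nearly none can be negative or indeterminate. A 20% failure rate describes a different population or a different threshold.
- **Exposed number.** Section 9.5 expects 60 live births in the exposed cohort. Testing 60 requires every one of them, while section 9.4.7 expects some mothers to decline.

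Section 7 cites humoral immune suppression in infant monkeys exposed to another drug of the class, and the FDA requirement names infant and childhood outcomes related to it. The antibody test is the protocol's laboratory measure of that question. If the comparison shows no difference and is read against a stated 82% power, it will look more reassuring than the planned data allow.

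**Working it through.** **Inputs.** N = 60 and 120, baseline 20%, RR 2 (hence 40% in the exposed), two-sided alpha 0.05: Table 3 and its footnote b. Sixty per group: section 9.4.7 and footnote k. The documents do not quantify how near to 100% the positive rate should be. A failure rate of 2% to 5% is assumed here to show the range.

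**Formula (normal approximation).** Power = Φ[(d − 1.96·s0)/s1], where d = p1 − p2, s0 = √[p̄(1 − p̄)(1/n1 + 1/n2)], s1 = √[p1(1 − p1)/n1 + p2(1 − p2)/n2], and p̄ is the average rate weighted by group size. The Fisher and uncorrected chi-square figures come from summing the exact binomial probabilities of all outcome tables that reach p ≤ 0.05.

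**Step 1: the plan's own figure, 60 v 120, 40% v 20%.**
p̄ = (24 + 24)/180 = 0.2667; s0 = √(0.1956 × 0.025) = 0.0699; s1 = √(0.24/60 + 0.16/120) = 0.0730.
Power = Φ[(0.20 − 0.1370)/0.0730] = Φ(0.862) = 80.6%. Exact chi-square gives 81.3% and Fisher 77.7%. The stated 82% is close to the chi-square result.

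**Step 2: one comparison group at a time, 60 v 60, 40% v 20%.**
p̄ = 0.30; s0 = √(0.21 × 2/60) = 0.0837; s1 = √(0.40/60) = 0.0816.
Power = Φ[(0.20 − 0.1640)/0.0816] = Φ(0.441) = 67.0%. Exact chi-square gives 68.4% and Fisher 60.0%. Reaching 80% would need 82 per group by the normal formula.

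**Step 3: the baseline implied by section 9.4.7, 60 v 60.**

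| Comparator v exposed | Chi-square | Fisher |
|---|---|---|
| 20% v 40% (RR 2) | 68.4% | 60.0% |
| 5% v 10% (RR 2) | about 17% | 8.8% |
| 2% v 4% (RR 2) | 7.2% | 1.1% |
| 2% v 22% (Table 3's 20-point difference) | 96.7% | 92.8% |

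By the normal formula, the relative risk detectable with 80% power at 60 v 60 is 2.18 at a 20% baseline (43.6% failing), 4.49 at 5% (22.4% failing) and 8.39 at 2% (16.8% failing).

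On the choice of test, section 9.7.2.2 switches to Fisher when at least a quarter of cells have expected counts below 5. That rule stands under baseline characteristics and may or may not govern outcomes. If it does, chi-square applies at 20% v 40% (smallest expected count 60 × 0.30 = 18). Fisher applies at 5% v 10% (60 × 0.075 = 4.5) and at 2% v 4% (60 × 0.03 = 1.8).

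**Step 4: exposed infants available.** 75 × 0.95 ≈ 71 observable pregnancies; 71 × (1 − 0.10 − 0.05) ≈ 60 live births. The target of 60 is therefore 60/60 = 100% uptake. No uptake rate is given. For assumed uptake of 80% and 50% in the exposed group only, at 20% v 40%, power is 64.7% (chi-square) or 57.2% (Fisher) for 48 v 60, and 52.4% or 46.7% for 30 v 60.

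**The case against.** The strongest reply has several parts.

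- **The 82% is not miscalculated.** This is right. The row's own inputs give 81%. What fails is their agreement with the rest of the protocol.
- **The pooling is disclosed.** Footnote k shows it, and the Amendment 1 entry in section 5 calls the 120 a combined number. Disclosure does not reconcile it with independent comparisons. Its effect alone is moderate: like for like by chi-square, 81% falls to 68%.
- **The comparison is not blind to immune suppression.** A reader might infer from the low-baseline figures that the binary endpoint cannot detect it. The documents do not support that. Carrying RR 2 to a 2% baseline shrinks a 20-point difference to 2 points. If the 20-point difference is kept, power is 93-97%.
- **Sixty is a target and recruitment may exceed plan.** Section 9.2.2 keeps enrolment open for 10 years even if 75 exposed pregnancies are reached early. More than 60 exposed live births is possible, but section 9.5 does not plan on it.
- **This is one secondary outcome in a voluntary sub-study**, and section 9.9 already concedes limited power. That lowers the stakes but does not make the stated figure right.

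Two further inferences are tempting. One is that eligible infants, who "will have had up to 3 diphtheria, tetanus, and pertussis scheduled immunizations", could be counted as failures for want of doses. The wording permits fewer than three, but vaccine administration is recorded and section 9.7.2.5.2 provides for confounder adjustment, so no error is stated. The other is that the continuous titre should replace the binary comparison. The endpoint is adequacy of response, which is a threshold idea, and section 9.4.7 already measures the titre continuously. Which scale leads is a choice for the analysis plan.

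**Conclusion.** The point holds as an inconsistency of inputs. The 82% applies only to a pooled comparator group of 120 and a 20% failure rate. The protocol plans separate comparisons with 60 per group and expects almost no failures.

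Removing the pooling alone takes power to about 68% (chi-square) or 60% (Fisher), below the 80% that section 9.5 claims. This step needs no outside assumption. If failure is also near zero, power for a doubling is about 7-17% (chi-square) or 1-9% (Fisher). That range rests on the assumed 2% to 5%.

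Low power here means low power for RR 2, not for every important effect. The mismatch between 60 tested and 60 exposed live births is real, but its effect on power cannot be fixed without an uptake rate. The 20% is attributed to a cited vaccine study, which could not be checked here.

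**What to change.** Restate the Table 3 row with 60 or fewer infants per comparison group, unpooled. Alternatively, say explicitly in sections 9.5 and 9.7.2.5.2 that the exposed group will be compared with Groups I and II combined. Reconcile the 20% baseline with the near-100% expectation in section 9.4.7, using the definition of inadequate response in section 9.7.2.5.2 (negative or indeterminate). Allow for uptake below 100% in the exposed group, with the assumed rate stated. Then give the resulting power or, more usefully at a low baseline, the detectable difference.

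Reporting the comparison of log titre beside the adequacy comparison is an optional supportive analysis, since the titre is already measured.

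The cost is a corrected table row and a few sentences, with no new data collection. The downside is a less favourable stated power.

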9.3.2.2.2 Infant Outcomes

- Rate and pattern of minor structural **birth** defects where a minor structural **birth** defect is defined as a structural anomaly (itemized on the study examination form) which has neither cosmetic nor functional significance to the child, and a pattern is defined as the same 3 or more minor structural **birth** defects in 2 or more children (see [Appendix A](#), 04.E. Dymorphology Exam Form). Due to the large variability in the sensitivity and specificity of identification of minor defects, in this study, minor defects are tabulated only in those infants who receive the study-related physical examination. This approach of assessment for clusters is based on prior studies that suggest 3 or more minor malformations is a meaningful cut point ([Leppig et al, 1987](#); [Méhes et al, 1973](#); [Marden et al, 1964](#)).
- Rate of small for gestational age where small for gestational age is defined as birth size (weight, length, or head circumference) \leq 10th centile for sex and gestational age using standard pediatric CDC growth curves for full term or preterm infants ([NCHS, 2000](#); [Olsen et al, 2010](#)).
- Rate of postnatal growth deficiency where postnatal growth deficiency is defined as postnatal size (weight, length, or head circumference) \leq 10th centile for sex and age using standard pediatric growth curves, and adjusted for postnatal age for premature infants if the postnatal measurement is obtained at less than 1 year of age.
- Rate of postnatal serious infections (see [Appendix D](#)) and hospitalizations as assessed throughout the 5-year postnatal follow-up period. Pediatric records will be requested after delivery and then on an annual basis with specific requests for documentation of serious infections and hospitalizations
- Rate of infant reactions to scheduled vaccinations as assessed throughout the 5-year postnatal follow-up period. Pediatric records and a questionnaire regarding vaccine administration according to recommended schedule and any vaccine-related adverse events will be obtained on an annual basis (see [Appendix A](#), 08.12. Vaccine Information Form).
- Infant response to IgG-tetanus antibody as a biological marker to evaluate humoral immune response. To be performed via a heel stick **or venipuncture** and standardized assay test between 6-12 months of age in a subset of infants in each of the study groups, conditional on the consent of the mother.

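### At the planned 75 exposed women, the immune sub-study's 60 exposed infants are every expected exposed live birth, so Table 3 makes no allowance for refusal and its 82% power is overstated unless uptake is complete or enrolment exceeds 75

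*Protocol*

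**What the plan says.** All references are to the protocol.

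- **Enrolment (section 9.5).** "An enrollment total of 75 in the exposed group and 150 in each of the 2 comparison groups after 10 years is anticipated". Section 9.2.2 calls 75/150 the minimum and keeps recruitment open for 10 years even if 75 exposed pregnancies are reached sooner.
- **Yield (section 9.5).** After 5% loss to follow-up, 10% spontaneous abortion or stillbirth and 5% elective abortion, the plan expects "an estimated 71 observable pregnancies of which 60 are estimated to result in live births in cohort 1 (exposed group"). Each comparison group is expected to yield 120 live births.
- **Sub-study (section 9.4.7).** "While it is anticipated that not all mothers will agree to this sub-study, a sample size of 60 in each group will be targeted". Section 9.3.2.2.2 describes the test as done "in a subset of infants in each of the study groups, conditional on the consent of the mother".
- **Table 3, inadequate immune response.** 60 exposed v 120 comparison infants, baseline 20%, relative risk 2, power 82%, two-tailed alpha 0.05. Footnote k explains the 120 as 60 infants per cohort.
- **Table 3, postnatal growth.** 46 exposed v 108 comparison infants, so this row already uses fewer than the 60 and 120 live births.

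**The concern.** The sub-study's exposed target equals the whole expected supply of exposed infants, and the sentence that sets it says some mothers will refuse. At planned enrolment both cannot be true. The postnatal growth row shows that the authors reduced N for a postnatal outcome elsewhere in the same table. The immune row, which needs the mother's agreement to a blood sample, has no reduction.

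This matters because humoral immune suppression is one of the safety questions behind the FDA requirement (section 7), and section 7 notes that it was not assessed in infant monkeys given evolocumab. A null tetanus-antibody result would be read against a stated 82% power that the plan does not support at its own enrolment figure.

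**Working it through.** **1. Live births (section 9.5).**
Exposed: 75 x 0.95 = 71.25, taken as 71; 71 x (1 - 0.10 - 0.05) = 60.4, taken as 60.
Each comparison group: 150 x 0.95 = 142.5, taken as 142; 142 x 0.85 = 120.7, stated as 120.
Both stated figures reproduce.

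**2. Uptake that the target implies.**
Exposed: 60/60 = 100%. Each comparison group: 60/120 = 50%.
Only the exposed group is affected.

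**3. The plan's own power, 60 v 120, 20% v 40%, two-sided 0.05.**
Normal approximation:
- pooled proportion = (60 x 0.40 + 120 x 0.20)/180 = 0.267
- SE under the null = sqrt(0.267 x 0.733 x (1/60 + 1/120)) = 0.0699
- SE under the alternative = sqrt(0.24/60 + 0.16/120) = 0.0730
- power = Phi((0.20 - 1.96 x 0.0699)/0.0730) = Phi(0.862) = 80.6%

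Exact power is the sum, over all pairs of event counts that the test rejects, of Bin(x; n1, 0.40) x Bin(y; n2, 0.20). It gives 77.7% with Fisher's exact test and 81.3% with the uncorrected chi-square test. The stated 82% is therefore roughly reproduced for 60 v 120, and the fault lies in the 60. The like-for-like baseline below is 77.7/81.3%, not 82%.

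**4. Allowing for refusal.** The protocol gives no uptake rate, so 95% to 60% is an assumption. Exposed N = uptake x 60; the comparison N is held at Table 3's 120.

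| Uptake | Exposed N | Exact power, Fisher / chi-square | Points lost from baseline |
|---|---|---|---|
| 100% | 60 | 77.7 / 81.3% | none |
| 95% | 57 | 76.4 / 80.1% | 1.3 / 1.2 |
| 90% | 54 | 75.4 / 78.7% | 2.3 / 2.6 |
| 80% | 48 | 71.6 / 76.7% | 6.1 / 4.6 |
| 70% | 42 | 68.3 / 71.9% | 9.4 / 9.4 |
| 60% | 36 | 63.9 / 67.0% | 13.8 / 14.3 |

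At 46 exposed infants, the protocol's own number for postnatal growth (46/60 = 77%), power is 70.2/74.8%.

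**5. Enrolment that would deliver 60 tested infants.** Women needed = 60/(uptake x 0.95 x 0.85): about 83 at 90% uptake, 93 at 80% and 106 at 70%.

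**The case against.** Several points on the other side have force.

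- **60 is a target and 75 a minimum.** A reader might infer that 60 exposed infants can never be reached. The protocol does not support that: Table 3 is headed as based on the minimal sample size, section 9.2.2 allows recruitment past 75, and section 9.5 has feasibility reviewed every year. The claim is limited to enrolment of 75. Still, 75 is what section 9.5 anticipates after the full 10 years, and Table 3 uses 60 as the N behind a power figure.
- **Attrition is partly counted already.** A reader might add further loss of infants before sampling. The 60 is already net of 5% loss to follow-up, and sections 9.2.6, 9.7.2.3 and 9.9 count that loss up to a year after the due date, which overlaps the 6 to 12 month sampling window. What clearly remains is refusal of the blood sample.
- **The loss may be small.** Section 9.4.7 gives three routes for collecting the sample. If uptake is 90% to 95%, power falls by only about 1 to 3 points. That stands, but the protocol offers no figure to show that uptake will be that high.
- **Much lower power can be computed against one comparison cohort.** For 48 v 60, exact power is 57.2/64.6%, and a reader might put this down to refusal. Most of the fall comes from footnote k's pooling: 60 v 60 gives only 60.0/68.4% at full uptake. That is a separate issue.
- **The preference for a spread of exposure lengths.** A reader might call this rule empty because every exposed infant is needed. It could operate if enrolment passes 75, and section 9.4.7 already offers the sub-study to all three cohorts, so no change to it is needed.
- **Limited reach.** This is one secondary outcome, and section 9.9 concedes modest power. That bears on the weight of the point, not on whether the row is right.

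**Conclusion.** The point holds at the planned enrolment. Sixty exposed infants in the immune row require every expected exposed live birth to be sampled, which section 9.4.7 itself does not expect. The exposed N and the 82% are overstated unless uptake is 100% or more than 75 exposed women enrol. At 95% uptake the chi-square figure only just stays above the 80% that section 9.5 promises; at 90% it does not, and Fisher's test is below 80% even with all 60. At 80% uptake the cost is about 5 to 6 points; at 60%, about 14.

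These sizes rest on the assumed uptake range, on Table 3's 20% v 40%, and on its 120 comparators. The primary analysis is not affected.

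**What to change.** In section 9.4.7, state an assumed uptake for blood sampling in the exposed cohort, with its basis. In the immune row of Table 3, set the exposed N to uptake x 60 (for example 48 at 80%, or 42 at 70%) and restate power or the detectable relative risk for that N. Use the comparator N that belongs to each separate comparison, since footnote k's 120 is 60 from each of two cohorts while section 9.5 compares each group with the exposed group independently. If the sponsor relies on enrolment beyond 75 to reach 60, say so and give the number required.

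The cost is a sentence in section 9.4.7 and one table row. No added enrolment is needed; the downside is a less favourable stated figure.
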